10.2. Sample Size Calculations

Sample size calculation done using G-power sample size calculator version 3.1.9.6 (Kang, 2021). The sample size calculation is based on the previous study by Minić and colleagues on the effect of the local probiotics in the therapy of periodontitis: a randomised prospective study (Minić, Pejčić, & Bradić-Vasić, 2022). The statistical test was set as “means: difference between two independent means (two groups)”, with an alpha error of 5%, and 90% statistical power. The minimum total sample size required is 12. Considering the probability of drop out rate 10%, 14 patients will be included.

$$\underline{12 + (12 \times 0.10) = 14}$$

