10.7. Group Allocations

Both right (quadrant 1 and 4) and left (quadrant 2 and 3) halves of all 14 participants, split mouth design will be assigned randomly to one of two treatment modalities via computer generated random sequence done by supervisor. A simple randomisation method will be employed to assign 14 participants into two groups (Group 1 and Group 2 corresponding to right halves: test and left halves: control or right halves: control and left halves: test) alternatively. A series of random numbers will be generated using the Numbers RAND() formula, done by supervisor, [name]. The RAND() function in Numbers produces uniformly distributed random numbers between 0 and 1. Fourteen unique random numbers will be generated, one for each participant in the study. The assigned random numbers will be sorted in ascending order from smallest to largest. This

step ensured that the patients will be arranged in a random sequence. Patients will then be assigned to two groups (Group 1 and Group 2) alternatively, starting with Group 1. This process will start with Group 1 and continue with Group 2, then back to Group 1, and so forth, until all patients were assigned to a specific group. The treatment allocation cards were sealed in envelopes until the clinical procedure.

The random allocations sequences will be concealed in a sequential sealed opaque envelope by [name] and will only be opened on the day of intervention's applications. Subgingival applications of either control drops and *Lactobacillus reuteri* probiotic drops will be done by [name].

Groups	Treatment
Control Halves	
On day 0, baseline record will be taken. Then, subjects will receive motivation and oral hygiene instructions on standard effective oral hygiene practice which include tooth brushing, flossing, interdental brush usage and single tufted brush, followed by professional mechanical plaque removal (PMPR) and root surface debridement (RSD). Following this, the control quadrants will be receiving application of the control drops (sterile distilled water) immediately after RSD together with post-operative instructions. Oral hygiene kit will also be given. ([name])
 
Reapplications of control drops together with oral hygiene review visit will be done on day 7, 14, 21 and 28 days after the first subgingival control applications. ([name])
 
Follow up visit for assessment of BoP, PPD, CAL, PI and GI will be done at 3 months interval from the baseline. ([name])

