10.9. Study Flow Chart

11. Statistical Analysis

All data will be collected in numerical form and will be analysed using the IBM SPSS Statistics Version 26.0 software. Histogram plot of data will be first used to check for normality of data distribution. Then, either Independent t-Test or Mann-Whitney Test will be used to compare data between two groups. The variables will be presented as mean and standard deviation for parametric test or median and interquartile range for non-parametric test. Significant level will be set at p-value $p < 0.05$. Meanwhile data within groups to evaluates statistically significant changes from baseline to follow up visits will be analysed either using Paired t-Test or Wilcoxon Signed Ranked Test.

Parameter	Visit	Control group	Test group	p-Value
BoP	Baseline			
	3 months			
PPD (mm)	Baseline			
	3 months			
CAL (mm)	Baseline			
	3 months			
PI	Baseline			
	3 months			
GI	Baseline			
	3 months			

Clinical Parameters for Groups 1 and 2 (mean \pm SD or median (IQR)) at different time intervals

(*denotes statistically significant difference, $p < 0.05$)

12. Budget

	Quantity	Cost/ Unit	Total Cost
Disposable syringe (1ml) (100's/ box)	1	RM 50.00	RM 50.00
Flexible tip (0.25mm) (100's/ box)	1	RM 200.00	RM 200.00
Gracey curettes	28	RM 209.25	RM 5859.00
Sharpening kit	1	RM 2442.00	RM 2442.00
Small cassette	3	RM 592.50	RM 1777.50
Lactobacillus reuteri probiotic	20	RM 134.50	RM 2690.00
Acrylic stents	20	RM 200.00	RM 4000.00
Oral hygiene kit	20	RM 100.00	RM 2000.00
		T O T A L COST	RM 19,018.50

13. Gantt Chart

	2023	2024				2025				2026			
	NOV- DEC	JAN- MAR	APR- JUN	JUL- SEP	OCT- DEC	JAN- MAR	APR- JUN	JUL- SEP	OCT- DEC	JAN- MAR	APR- JUN	JUL- SEP	OCT- DEC
Drafting proposal													
Defence of research proposal (DRP)													
Ethics application													
Data collection preparation													
Data collection													
Thesis write-up													
Submission research paper													
Thesis submission for viva													
Research sends for publication													

14. References

- Chandran, Arunah. (2020). National Diabetes Registry Report, 2013-2019. Ministry of Health Malaysia. https://www.moh.gov.my/moh/resources/Penerbitan/Rujukan/NCD/Diabetes/National_Diabetes_Registry_Report_2013-2019_26082021.pdf

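### The planned test-versus-control comparison uses neither the patient pairing nor the randomised side order; a paired analysis by side order would recover the lost precision

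*Combined protocol and SAP*

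**What the plan says.** Section 10.4 describes a split-mouth trial, so each patient supplies one test half and one control half. What is randomised is which side receives which treatment. Section 10.7 will "assign 14 participants into two groups (Group 1 and Group 2 corresponding to right halves: test and left halves: control" in one group, with the reverse in the other. Fourteen random numbers are sorted and patients are then assigned alternately, starting with Group 1, which gives 7 patients per side order.

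For test versus control, section 11 states: "Then, either Independent t-Test or Mann-Whitney Test will be used to compare data between two groups". Paired tests appear there only for change from baseline within a treatment. No patient, side or side-order term is mentioned. The results table has control and test columns, but its caption reads "Clinical Parameters for Groups 1 and 2", the name that section 10.7 gives to the side orders.

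**The concern.** The analysis does not follow the randomisation, in two respects.

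- **Pairing.** The two halves of one mouth share a patient. An independent test treats them as unrelated and leaves the between-patient variation in the standard error, although the split-mouth design exists to remove it.
- **Side order.** If right and left halves differ in outcome, that difference enters the test-minus-control contrast with a plus sign in Group 1 and a minus sign in Group 2. At 7:7 it cancels from the mean but stays in the spread. A sponsor who repaired only the pairing would still carry it in the error term.

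At stake is precision in a trial of 14 patients: a useful effect could be missed or estimated with a needlessly wide interval. Unequal dropout between the side orders would also shift the estimate in that realised sample.

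**Working it through.** **The plan's own figures.** Section 10.2 uses "means: difference between two independent means (two groups", "with an alpha error of 5%, and 90% statistical power", and arrives at 12 in total. The dropout step reproduces: 12 × 1.10 = 13.2, and 12/0.90 = 13.3; both round up to 14. The 12 cannot be reproduced because no effect size or SD is given. Working backwards with noncentral-t power, 6 per group at 90% power implies an effect of about 2.08 SD two-sided or 1.82 SD one-sided.

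**Inputs.** From the documents: n = 14 patients; 7:7 side orders (derived from the alternation); alpha 5%, taken as two-sided. Assumed, because not given: within-patient correlation ρ = 0.5 or 0.8; right-minus-left difference d = 0 to 0.75, in SDs of the paired difference; a true effect of 1 such SD as a power benchmark.

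**Model.** For each patient, test minus control = δ + d·g + error, with g = +1 in Group 1 and −1 in Group 2.

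**Step 1: pairing, with d = 0.** With outcome SD σ per half:

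- SE used by the independent test: σ√(2/14) = 0.378σ.
- True SE: σ√(2(1−ρ)/14) = 0.267σ at ρ = 0.5 and 0.169σ at ρ = 0.8.
- Ratio: 1/√(1−ρ) = 1.41 and 2.24.

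In simulation (200,000 runs per setting) power is about 79% (ρ = 0.5) or 27% (ρ = 0.8) for the independent t-test, against 93% paired. The type I error of the independent test is 0.8% or below.

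**Step 2: side order left out of a paired test, 7:7.**

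- SE inflation: √(1 + (14/13)d²) = 1.033, 1.127, 1.267 for d = 0.25, 0.5, 0.75.
- Critical t: 2.160 (13 df) without side order, 2.179 (12 df) with it.
- CI ratio: inflation × 2.160/2.179.

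| d | CI width, plain paired / with side order | Type I error, plain paired | Power at 1 SD, plain paired |
|---|---|---|---|
| 0 | 0.991 | 5.0% | 93% |
| 0.25 | 1.024 | 4.3% | 92% |
| 0.5 | 1.117 | 3.0% | 89% |
| 0.75 | 1.256 | 1.5% | 83% |

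With side order included, type I error is 5% and power 93% in every row. Break-even on interval width is at about d = 0.13.

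**Step 3: the same side difference under the test actually planned.** It adds ((d·SD of the paired difference)²/4)(14/13) to each arm's variance, where the SD of the paired difference is σ√(2(1−ρ)). The SE rises by about 1%, 3% and 7% at ρ = 0.5, and by about 0.3%, 1.3% and 3% at ρ = 0.8. Most of the cost in step 2 therefore appears only once the pairing is repaired.

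**Step 4: unequal dropout.** The unadjusted mean is off by d(n₁ − n₂)/(n₁ + n₂): zero at 7:7 and 6:6, d/13 at 7:6, d/6 at 7:5. At 7:5 that is 0.042, 0.083 and 0.125 SD, against an SE of 1/√12 = 0.289 SD. If two of the 14 leave at random, the chance of a 7:5 or 5:7 split is 2 × 21/91 = 46%. The analysis with side order is unbiased at any split.

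**The case against.** The strongest case against is that side order is a minor matter beside the pairing. That stands: step 3 shows that it hardly affects the planned independent test, and it is best handled as part of the pairing repair. It still needs saying, because a change to a plain paired test would leave it out.

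The size rests on an unknown. No section gives a right-left difference, one clinician debrides both sides, and a persistent difference such as one from the brushing hand would largely cancel in change scores. This stands too: at d = 0.25 the loss is negligible, and at d = 0 the side term costs slightly. Section 11 compares values at each visit, however, so nothing in the present plan removes a persistent side difference.

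The 1-SD benchmark is also a choice. At the 2.08 SD implied by the stated 12, taken as SDs of the paired difference, power is essentially 100% with or without the side term. That weakens the power argument but not the one about interval width, and the plan does not state that effect.

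A reader might infer three stronger things that the documents do not support:

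- **More false positives.** The error that grows is the residual error; type I error falls below 5%.
- **A systematically biased trial.** The shift belongs to a realised unequal split and averages to zero over repeated trials if dropout is unrelated to side order.
- **A plan to compare the side orders in place of the treatments.** The table columns are control and test, so the caption is a labelling fault only.

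**Conclusion.** The concern holds as a loss of precision. The larger part is the ignored pairing: about 79% or 27% power in place of 93%, for ρ = 0.5 or 0.8 and an assumed 1-SD effect. The smaller part is side order, which matters once the analysis is paired: an interval 2% to 26% wider for d between 0.25 and 0.75, and no gain from adjusting if d is zero. Both ρ and d are assumptions, so these figures are ranges and not predictions for this trial. The d/6 shift at 7:5 is conditional on that split and is less than half of one SE throughout the range considered. The change is worth making because one analysis repairs both faults at almost no cost.

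**What to change.** In section 11, replace the independent test between halves with a paired analysis that includes side order:

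1. For each patient and outcome, compute the right-half minus left-half difference.
2. Compare Group 1 with Group 2 on that difference by the Independent t-Test, with Mann-Whitney as the rank version. The Group 1 mean estimates d + δ and the Group 2 mean d − δ.
3. Report half the difference between the two group means, with both confidence limits halved, as the test-control effect. Equivalently, regress test minus control on an intercept and a +1/−1 group term.
4. Relabel the results table as control and test halves.

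Apply this to the 3-month values. If the sponsor prefers change from baseline, state that as a separate change, since section 11 now compares baseline and 3-month values separately.

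The cost is a rewording of section 11 and one degree of freedom (critical t 2.179 in place of 2.160, an interval 0.9% wider if d = 0). The software and the named tests stay, and no new data are needed.

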6.1. General Objective

This study is to evaluate the effectiveness of local delivery of *Lactobacillus reuteri* probiotic on periodontitis patients with type 2 diabetes mellitus, as an adjunct to non-surgical periodontal treatment.

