10.4. Study Design

This is a single blinded, prospective, randomised split-mouth clinical trial, where quadrants will be divided randomly into control and test groups.

Baseline records of periodontal clinical parameters will be taken for all subjects which include; bleeding on probing index (BoP), probing pocket depth (PPD), clinical

attachment level (CAL), plaque index (PI) and gingival index (GI). All the clinical records will be kept in locked case and delivered after the end of the clinical trial. University of North Carolina (UNC-15) probe will be used to measure the periodontal pocket depth and CAL.

All patients, after the baseline parameters recorded, will then receive motivation and oral hygiene instructions on standard effective oral hygiene practice which include tooth brushing, flossing, interdental brush usage and single tufted brush, followed by full mouth root surface debridement (RSD) under local anaesthesia on all teeth with pocket of ≥ 5 mm (Heitz-Mayfield, 2005; Matesanz-Pérez et al., 2013) using ultrasonic scaler and Gracey's curette, until the root surface feels smooth and clean to an explorer tip of UNC-15 probe (Kaner et al., 2007). For each patient, complete full mouth professional mechanical plaque removal (PMPR) and RSD will be done within 24 hours. All these will be done by main examiner, [name].

Both right (quadrant 1 and 4) and left (quadrant 2 and 3) halves will be assigned randomly to one of the two treatment modalities. A simple randomisation method will be employed to assign 14 participants into two groups (Group 1 and Group 2 corresponding to right halves: test and left halves: control or right halves: control and left halves: test) alternatively. A series of fourteen unique random numbers will be generated using the Numbers RAND() formula, one for each. Patients will then be alternately assigned to Group 1 and Group 2, starting with Group 1, done by supervisor, [name]. The treatment allocation cards will be sealed in envelopes until the clinical procedure.

The subgingival applications of either control (sterilised distilled water) or test (*Lactobacillus reuteri* probiotic) drops will be done based on the randomisation sequences done by [name] before. The allocated group for every subject will only be told to [name] on the

[figure not shown]

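### Section 11 plans no within-patient test-minus-control difference or confidence interval, and its unpaired p-value and per-arm SDs cannot show how precisely that difference is estimated.

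*Combined protocol and SAP*

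**What the plan says.** Section 10.4 sets the design: "This is a single blinded, prospective, randomised split-mouth clinical trial". Section 10.7 confirms that one side of each mouth is test and the other control, so every comparison of treatments is made within a patient. The specific objectives in section 6.2 are five such comparisons at 3 months: BoP, PPD, CAL, PI and GI.

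For the comparison of treatments, section 11 says: "Then, either Independent t-Test or Mann-Whitney Test will be used to compare data between two groups". Paired methods appear only for change over time inside each arm: "Meanwhile data within groups to evaluates statistically significant changes from baseline to follow up visits will be analysed either using Paired t-Test", or its Wilcoxon counterpart. The descriptive output is "The variables will be presented as mean and standard deviation for parametric test or median and interquartile range for non-parametric test".

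The table shell in section 11 has a column for each arm and one for the p-value, with rows for baseline and 3 months, and an asterisk for results with p below 0.05. It has no column for a difference or an interval, and neither is planned elsewhere. The protocol does not say how a non-significant result will be interpreted.

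**The concern.** The quantity that answers the objectives is the test-minus-control difference within a patient, together with its uncertainty. The plan names no estimator for it. In a paired design the spread of that difference depends on how strongly the two halves of a mouth agree, and nothing in the planned output carries that information.

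The trial has at most 14 pairs, so imprecision is a real possibility. A table of arm summaries and significance marks does not let a reader tell a small effect estimated well from an effect too poorly estimated to judge. A significant result would likewise come without an interval showing which effect sizes remain plausible.

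**Working it through.** **The plan's own figure.** Section 10.2 gives a minimum of 12, for two independent means "with an alpha error of 5%, and 90% statistical power". It cannot be rebuilt forwards, because no effect size, SD or sidedness is stated. Solving backwards with the non-central t, 6 per group and 90% power require a standardised difference of about 2.08 (two-sided) or 1.82 (one-sided). The dropout step does reproduce: 12 + 1.2 = 13.2, rounded up to 14.

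**Inputs for the precision check.** There are n = 14 pairs, or 12 if two patients are lost (section 10.2). The correlation ρ between halves is not in the documents, so it is an assumption shown over a range. Results are in units of the SD of a half-mouth score, taken as equal in both arms.

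**Formula.** The SD of the within-patient difference is SD × √(2(1 − ρ)). The 95% half-width is t(0.975, n − 1) × that SD / √n. For n = 14, t = 2.160 and 2.160/√14 = 0.577. For n = 12, t = 2.201 and 2.201/√12 = 0.635.

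| Assumed ρ | SD of difference | Half-width, 14 pairs | Half-width, 12 pairs |
|---|---|---|---|
| 0 | 1.414 | 0.82 | 0.90 |
| 0.5 | 1.000 | 0.58 | 0.64 |
| 0.8 | 0.632 | 0.37 | 0.40 |
| 0.9 | 0.447 | 0.26 | 0.28 |

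Identical printed means and SDs are thus compatible with roughly a threefold range of precision (0.82/0.26 ≈ 3.2).

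**Why the p-value does not help.** The independent t statistic depends only on the two means, the two SDs and n. Suppose the table showed a difference of 0.5 SD with 14 patients. Then t = 0.5/√(2/14) = 1.32 on 26 degrees of freedom, and p = 0.20 whatever ρ is. The paired interval would be 0.5 ± 0.577, or −0.08 to 1.08, at ρ = 0.5. It would be 0.5 ± 0.365, or 0.13 to 0.87, at ρ = 0.8. One printed row fits both an inconclusive result and one that excludes zero. The within-arm tests do not fill the gap, since they use the agreement of a half with its own baseline and not with the opposite half.

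**An interval built from the arm SDs as if independent.** The half-width is t(0.975, 26) × √(2/14) = 0.78 SD for n = 14. The paired values are 0.68 at ρ = 0.3 and 0.45 at ρ = 0.7.

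**Median and IQR branch.** The difference between two medians is not in general the median of the within-patient differences, so the point estimate cannot be derived either.

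**Effect of changing the test (illustration).** The assumptions are 14 pairs, normal data, a true effect of 0.5 arm SD, and ρ from 0.3 to 0.7. Power of the planned independent t-test (simulated) goes from 21% to 14% across that range, and its type I error from 2.1% to 0.1%. Power of the paired t-test goes from 31% to 61%.

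**The case against.** The strongest reply is that a point estimate is available. Both halves come from the same patients, so with complete pairs the difference between the printed means is exactly the mean within-patient difference. This is correct for the parametric branch. A reader might infer that the trial cannot say how large the effect is; the documents do not support that where means are printed. What is missing there is a prespecified estimate and its precision.

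A second reply is that the lost precision comes from the choice of an unpaired test. Had the halves been compared with a paired t-test, the mean difference and an exact p-value would give back the interval. This also stands, and it is why an extra column alone would not be enough: an interval taken from the independent test would be wrong for this design.

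A third is that a null result need not be expected. A reader might infer from the small sample that one is likely. That depends on the true effect, which the documents do not state. At the 2.08 SD implied by 12 patients, power with 14 is close to 100%; only for small to moderate effects is a null probable. Section 9 cites one study of local application with no significant difference and one pilot with a favourable result.

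Finally, nothing in the documents says that a non-significant result will be reported as lack of effectiveness. That is a risk of significance-only reporting, not a stated rule.

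**Conclusion.** The point holds as a gap in both analysis and reporting. Section 11 plans no within-patient test-minus-control difference and no interval, and the unpaired test removes the one route by which a reader could have reconstructed the precision. With 14 pairs, what stays hidden is a half-width anywhere from 0.82 down to 0.26 arm SD for correlations of 0 to 0.9. These values assume equal arm SDs and roughly normal differences, and the correlation itself is not in the documents. The absence of the estimate and interval is plain from section 11 and does not rest on those assumptions. The conclusion goes no further than this: a non-significant result could be mistaken for no effect. It does not say that a null is likely, or that the size of the effect is wholly unobtainable.

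**What to change.** - For each of the five outcomes at 3 months, replace the p-value column with three items from a paired analysis of the halves: the within-patient test-minus-control difference, its 95% confidence interval, and p.
- Use the mean difference with the paired t-test, or the Hodges-Lehmann estimate with the Wilcoxon signed-rank test where the non-parametric branch applies. These take the place of the independent t-test and Mann-Whitney test.
- Add a sentence that p ≥ 0.05 alone is not evidence of no effect and that the interval is to be read.

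Do not tie that sentence to the effect size behind section 10.2. None is stated there. If the back-solved 2.08 SD were used, then in simulation with 14 pairs, a true effect of 0.5 arm SD and ρ from 0 to 0.7, at least 99% of non-significant results would have an interval excluding it. They would so escape being called inconclusive. A rule of that kind would first need a relevant difference stated and justified by the sponsor.

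The cost is a changed between-half test, one changed table column and a few sentences. No new data are needed. SPSS paired t-test output already gives the mean difference and its interval.

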A systematic review conducted recently demonstrated a positive impact when employing a combined probiotic containing two strains of *Lactobacilli reuteri* systemically alongside scaling and root planing (Martin-Cabezas et al., 2016). Furthermore, it was demonstrated that the utilisation of these probiotic lozenges resulted in a statistically significant and more substantial decrease in *Porphyromonas gingivalis* (Teughels et al., 2013) and in the proportions of obligate anaerobes for a period of up to 180 days (Tekce et al., 2015). However, despite all these, the study of *Lactobacillus reuteri* as an adjunct in treating patients with type 2 diabetes mellitus and periodontal disease with deep pockets is none to be found yet.

4. Research Questions

1. Does the application of *Lactobacillus reuteri* probiotic subgingivally in periodontal pockets after root surface debridement (RSD) results in significant improvement of

bleeding on probing (BoP) among patients with type 2 diabetes mellitus and periodontal disease?

2. Does the application of *Lactobacillus reuteri* probiotic subgingivally in periodontal pockets after root surface debridement (RSD) results in significant improvement of probing pocket depth (PPD) among patients with type 2 diabetes mellitus and periodontal disease?

3. Does the application of *Lactobacillus reuteri* probiotic subgingivally in periodontal pockets after root surface debridement (RSD) results in significant improvement of clinical attachment level (CAL) among patients with type 2 diabetes mellitus and periodontal disease?

4. Does the application of *Lactobacillus reuteri* probiotic subgingivally in periodontal pockets after root surface debridement (RSD) results in significant improvement of plaque index (PI) among patients with type 2 diabetes mellitus and periodontal disease?

5. Does the application of *Lactobacillus reuteri* probiotic subgingivally in periodontal pockets after root surface debridement (RSD) results in significant improvement of gingival index (GI) among patients with type 2 diabetes mellitus and periodontal disease?

5. Hypothesis

We hypothesise that the local delivery of *Lactobacillus reuteri* probiotic on periodontitis patients with type 2 diabetes mellitus, as an adjunct to non-surgical periodontal treatment may have a beneficial effect on the clinical parameters (BoP, PPD, CAL, PI and GI).

6. Objectives

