day of applications. Post-operative instructions will be given after the applications to all subjects. Each subject will also be given the same oral hygiene kit containing soft bristle toothbrush, single tufted brush, interdental brush, fluoridated toothpaste and dental floss. The applications will be repeated again in both groups after initial applications on every 7, 14, 21 and 28 days (Sufaru et al., 2022), all by student [name].

Follow up visit to evaluate all clinical parameters will be done on every subject, at three months (Segelnick & Weinberg, 2006) after treatment (RSD) by main examiner, [name].

[figure not shown]
10.5. *Lactobacillus Reuteri* Probiotic Applications

The subgingival applications of control (sterilised distilled water) and test (*Lactobacillus reuteri* probiotic) drops will be done after RSD on all pockets of $\geq 5\text{mm}$ (Matesanz-Pérez et al., 2013; Passariello et al., 2012), on each groups, in the same day after RSD completion. The subgingival applications will be done using 1mL disposable syringe attached with blunt soft Intra Vascular cannula tip (22 Gauge). Isolation will be done using cotton roll and saliva suction will be used to avoid saliva contaminations as possible. The control/ *Lactobacillus reuteri* probiotic drops will be introduced into the pocket, until overfill is observed at the gingival margin (Griffiths et al., 2000; Unsal et al., 1994). Subjects will then be instructed not to eat, drink or rinse for at least 30 minutes. Only tooth brushing will be instructed to subject and to avoid sticky food and chewing hardly on the applied area. The control and *Lactobacillus reuteri* probiotic drops applications will be repeated every 7, 14, 21, and 28 days (Sufaru et al., 2022), following the same duration procedure. Oral hygiene instruction will also be re-emphasised on each

visit. Follow up visit for assessment of clinical parameters (BoP, PPD, CAL, PI and GI) will be done at 3 months interval for both groups.

Picture showing example of acrylic stent with marking. *Journal of Indian Society of Periodontology - Vol 13, Issue 2*

Picture showing a 1mL disposable syringe attached with blunt soft flexible tip (0.25mm) which will be used for subgingival applications of control and *Lactobacillus reuteri* probiotic drops.

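### Five equal outcomes, each compared at p < 0.05 with no primary outcome: about a 15-23% chance of some false significant difference under valid paired tests, which the planned unpaired test may mask

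*Combined protocol and SAP*

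**What the plan says.** Section 4 asks five parallel research questions, one per clinical parameter, and section 6.2 repeats them as five between-group comparisons at 3 months. The hypothesis in section 5 is that the probiotic "may have a beneficial effect on the clinical parameters (BoP, PPD, CAL, PI and GI"). None of the five is ranked above the others.

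For the between-group comparison, section 11 states that "either Independent t-Test or Mann-Whitney Test will be used to compare data between two groups", with the rule "Significant level will be set at p-value" below 0.05. The results table lists all five parameters at baseline and 3 months with a p-value column, and its footnote reads "denotes statistically significant difference, $p < 0.05". Section 11 also plans baseline-to-follow-up tests within each group.

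Section 10.2 sizes the trial "with an alpha error of 5%, and 90% statistical power", citing an earlier study of local probiotics. It does not say which outcome, effect size or standard deviation was used. Section 10.4 describes the design: "This is a single blinded, prospective, randomised split-mouth clinical trial".

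No section gives a primary outcome, a testing order, an adjustment for multiple testing, the sidedness of the tests, or a rule for how many parameters must be significant before effectiveness is concluded.

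**The concern.** A stated alpha of 5% describes one test. Here five outcomes can each yield a significant result and nothing fixes in advance which of them decides the question. In a trial of 14 patients, whichever parameter crosses 0.05 could become the headline, and the choice could be made after the results are seen. The alpha and power in 10.2 give no protection because they cannot be attached to any of the five.

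The table and the within-group tests together produce 5 x 2 + 5 x 2 = 20 p-values. Only the five between-half comparisons at 3 months answer the stated objectives, so only those five are counted below.

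**Working it through.** **Inputs**
- Five outcomes, one follow-up at 3 months (sections 6.2 and 10.5).
- 0.05 per test, no adjustment (section 11).
- 14 patients, each giving one test half and one control half (sections 10.2 and 10.4).
- Two-sided testing: assumed, because section 11 speaks of a difference and gives no direction.
- Correlation between outcomes: not given. A common value of 0 to 0.7 is assumed, with higher values shown.
- Correlation between the two halves of a mouth: not given. Values of 0 to 0.7 are assumed.

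**1. The plan's own figure.** 12 + 12 x 0.10 = 13.2, rounded up to 14, so that step reproduces. The 12 can be neither reproduced nor refuted without an effect size and standard deviation. Six per group at 90% power needs a standardised difference of about 2.08 (two-sided) or 1.82 (one-sided).

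**2. Independent outcomes, valid tests.**
- Any false significant difference: 1 - 0.95^5 = 1 - 0.774 = 22.6%.
- A false difference favouring the probiotic (2.5% per two-sided test): 1 - 0.975^5 = 1 - 0.881 = 11.9%.

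**3. Correlated outcomes, valid tests.** For five normal statistics with common correlation ρ, shared component X and c = 1.96, the chance of at least one rejection is

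1 - E[{Φ((c - √ρ X)/√(1-ρ)) - Φ((-c - √ρ X)/√(1-ρ))}^5].

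Dropping the second Φ term gives the chance of at least one rejection favouring the probiotic. Paired t-tests with 14 patients were also simulated.

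| Outcome correlation | Either direction, normal | Either direction, paired t | Favouring probiotic, normal | Favouring probiotic, paired t |
|---|---|---|---|---|
| 0 | 22.6% | 22.6% | 11.9% | 12.0% |
| 0.3 | 20.9% | 21.1% | 10.5% | 10.7% |
| 0.5 | 18.3% | 19.0% | 9.2% | 9.5% |
| 0.7 | 14.8% | 15.4% | 7.4% | 7.7% |
| 0.8 | 12.7% | 13.4% | 6.4% | 6.7% |

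At 0.9 the normal figures are 10.2% and 5.1%. With 12 patients the paired t-test gives 22.7% at correlation 0 and 15.8% at 0.7 (either direction).

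**4. The test actually planned.** If the halves correlate at r, the variance of the difference in means is 2σ²(1-r)/n, but the independent t-test uses 2σ²/n. For positive r the test rejects too rarely. Simulated with 14 patients, either direction:

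| Between-half correlation | One outcome | Five outcomes, outcome correlation 0 | 0.5 | 0.7 |
|---|---|---|---|---|
| 0 | about 5% | 22.6% | 18.5% | 15.1% |
| 0.3 | about 2.1% | 10.3% | 8.6% | 7.2% |
| 0.5 | 0.8-0.9% | 4.2% | 3.6% | 3.1% |
| 0.7 | about 0.1% | 0.7% | 0.7% | 0.6% |

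The Mann-Whitney alternative was not simulated.

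**5. After a change.** One primary outcome tested by a valid paired two-sided test at 0.05 has a false-positive rate of 5% in either direction and 2.5% in favour of the probiotic. For comparison, Bonferroni over all five at 0.05/5 = 0.01 gives 1 - 0.99^5 = 4.9% if the outcomes are independent.

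**The case against.** Four arguments can be made for the plan.

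**The planned test may already be conservative.** This stands. With a between-half correlation of 0.5, the error over all five outcomes is 3-4%, below 5%. A reader might infer that 15-23% is the error rate of the analysis as written; the documents do not support that unless the halves are nearly uncorrelated. It is not a defence of the plan, however. One fault offsets another by an amount that depends on a correlation nobody has stated, and correcting the pairing removes the offset.

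**The larger figure is not the chance of a false benefit.** This also stands. A reader might take 15-23% as the probability of wrongly claiming that the probiotic helps. That range counts differences in either direction. For benefit alone it is about 7-12%, and the right comparator is 2.5%. One-sided tests at 0.05 would give 22.6%, 16.6% and 13.5% for benefit at outcome correlations 0, 0.5 and 0.7, but the documents do not state one-sided testing.

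**The five questions are posed separately, so 5% for each is enough.** This is a possible reading. It is equally tempting to say that significance on any single parameter would satisfy the hypothesis, but section 5 states no such rule. The documents fix neither reading, and that absence is the defect: one general objective on effectiveness (6.1) is to be judged from five results with no rule linking them.

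**Correlated outcomes reduce the problem.** True, and the table shows by how much. Even at 0.9 the either-direction figure is about twice the nominal 5%.

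**Conclusion.** The concern holds in this form: five co-equal outcomes are each tested at 0.05, without a primary outcome, an adjustment or a rule for concluding effectiveness, and the alpha and power in 10.2 belong to no named outcome.

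Under valid paired two-sided tests, with outcome correlations assumed between 0 and 0.7, the error is roughly three to five times that of a single test, whether counted in either direction or in favour of the probiotic only. As the analysis is now written, the actual rate is unknown and could lie above or below 5%. At assumed between-half correlations it is about 7-10% (0.3), 3-4% (0.5) or under 1% (0.7). The missing primary outcome is certain from the text; the size rests on the assumed correlations. The plan should be changed on this point, together with the pairing.

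**What to change.** Before outcome data are analysed:

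1. Name one primary outcome. PPD at 3 months, test half against control half within patient, has the best support: section 3 frames the problem around deep pockets, and section 9 quotes pocket depth as the result of the study used for sample size.
2. State which sites are averaged, for example the treated sites with baseline PPD of 5 mm or more. Section 10.6 gives an averaging rule for BoP, PI and GI but none for PPD.
3. Test it with a paired two-sided test at 5%. Without the pairing, the stated 5% would not be delivered.
4. Make CAL, BoP, GI and PI secondary, with 95% confidence intervals and Holm-adjusted p-values across the four.
5. State in sections 5 and 11 that the effectiveness conclusion rests on the primary outcome, and in 10.2 which outcome, effect size and standard deviation gave the figure of 12.

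The cost is wording only: no extra patients, visits or measurements. The downside is that a positive result on a secondary parameter alone can no longer carry the conclusion.
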